**STUDY SYNOPSIS**

Sponsor / Sponsor-Investigator	Bernafon AG
Study Title:	A clinical investigation comparing a standard hearing aid fitting protocol and a fitting protocol optimized for musicians
Short Title / Study ID:	BF006-1902
Protocol Version and Date:	2019.08.27; Version 2.0
Trial registration:	SNCTP; EudraCT
Study category and Rationale	Category A; Medical Device with CE Mark
Clinical Phase:	Post-market; Medical device study involving human subjects

Background and Rationale:	
The intended use of hearing aids is to amplify sounds to compensate for hearing loss. The initial goal is to amplify speech and facilitate understanding speech especially in noise. Research shows that wireless hearing aids are efficacious for older adults (Humes et al. 2017), and in general, an increase in satisfaction and substantial benefits are characteristic for the wireless hearing aids brought to market during the last decade.
 
Music is proven to enhance the lives of older people (Cohen et al., 2002; Lehmberg & Fung, 2010), but many people report a reduction in their ability to enjoy music with a hearing loss (Leek et al., 2008; Creech et al., 2013). Amplification can be used to overcome a hearing loss and return the joy of music to those with hearing loss. However, for listening to music or particularly, for musicians that play an instrument, the hearing aid settings used for amplifying speech often have adverse effects on music.
 
Hearing perception abilities are different for normal hearing people compared to hearing-impaired, and musical training (i.e. history of playing an instrument or singing) further alters the perception and listening preferences. Normal hearing listeners and those with musical training prefer less compression, meaning less signal processing. While hearing-impaired participants may not strongly favor one condition over the other (Mussoi et al., 2015). For people using hearing aids, music should be treated as a special signal and a program devoted to music listening is recommended (Chasin & Russo, 2004). However, it is not possible to predict in advance the properties of the music signal as it can't be generalized like speech (different instruments, style, musical setup). For musicians the dedicated program may require further optimization and fine-tuning specific to their instrument and/or the situations in which they play music.
 
For this study, Bernafon AG will carry out testing with participants with hearing loss to compare dedicated music programs. The current study will compare the standard music program available in the software to one that is fine-tuned for each participant. The Bernafon hearing aids used for the current study are CE- marked and have been on the market for almost one year. The goal is to determine whether musicians will perceive a difference and prefer a fine-tuned music program over the default music program in real-life situations.

Objective(s):	The purpose of this study is to compare the standard fitting protocol for hearing devices with a protocol that is optimized for musicians. Sound quality, specifically for playing music, should be improved with the optimized fitting.

Outcome(s):	
Primary Endpoint: The primary objective is to assess whether the optimized fitting is better than the standard fitting. At the end of the trial the participants will complete a preference questionnaire and choose a preferred program (optimized music or default music) including the reasons for their preference.
 
Secondary Endpoints: The secondary objective is to measure sound perception in a lab test in the clinic. The subjects will rate the perception of various aspects of music using both music programs.
 
The overall sound quality and benefit from the device will be measured with product questionnaires that ask the subjects to rate the hearing aids in specific situations after using them during field tests.
 
Safety Endpoint: The study aims to find any new risk factors and to ensure the safety of the device by monitoring all AEs.

Study design:	
This is a controlled, single blinded, comparative clinical evaluation conducted monocentric at the premises of Bernafon AG in Bern, Switzerland.

Inclusion / Exclusion criteria:	
Inclusion Criteria:
 
 
• All classifications of hearing loss (sensorineural, conductive, mixed)
 
• If the hearing loss is conductive or mixed it must be approved for amplification by a physician
 
• All shapes of hearing loss (flat, sloping, reverse slope, notch)
 
• Severity ranging from mild to profound
 
• German or French speaking
 
• Play a musical instrument
 
• Both genders
 
• Ages 18 and older
 
• Ability and willingness to sign the consent form
 
 
Exclusion Criteria:
 
 
• Normal hearing
 
• Contraindications for amplification
 
• Active ear disease
 
• Don't play an instrument
 
• Inability to follow the procedures of the study due to language problems, psychological disorders, dementia, or other cognitive problems of the participant
 
• A reduced mobility making them unable to attend weekly study appointments
 
• A reduced ability to describe auditory impressions and the usage of the hearing aids
 
• Uncooperative so that it is not possible to record a valid pure tone audiogram
 
• A strongly reduced dexterity
 
• Central hearing disorders
 
• Bernafon employees
 
• Family members of Bernafon employees
 

Measurements and procedures:	
Amplification is verified and compared with targets using Real Ear Measurements
 
Music perception is tested with a rating scale that asks the participants about various aspects of recorded music and is performed in a sound studio as a lab test.
 
Subjective performance of devices is tested with questionnaires asking the participants to rate aspects concerning the sound quality of the hearing devices.
 
Preference testing allows the participant to choose the program that they prefer, which rates the fitting protocol (standard vs optimized).

Study Product / Intervention:	
Viron 9 MNR
 
The investigational medical device (IMD) will be the Viron 9 hearing instrument. The hearing aid was released to the market in early 2019. Hearing instruments are worn approximately 10 hours per day and removed at night. The participants will wear the devices for two field periods of 10 +/- 7 days. They will be current or new hearing aid users.
 
There is no RMD as the comparison for the study is made using the same device. As the goal is to test fitting protocols, one device can be fitted with different programs within the same device. Participants can switch between the various programs to test them simultaneously in the situations in which they find themselves. The software version used during testing will be the final version of the software that was released to the market at the same time as the hearing aids.

Control Intervention (if applicable):	
The control is the program with the standard fitting (default music) protocol.

Number of Participants with Rationale:	
There will be an exploratory analysis of the data only. Based on the sample size calculation, the total number of participants will be approximately 18-20.

Study Duration:	
Approximately 5 months.
 
The screening of participants is planned for October 2019, and the final data collection appointments should occur in February 2020.

Study Schedule:	
Planned First-Participant-in: October 2019
 
Planned Last-Participant-Out: February 2020

Investigator(s):	
[name], Research Audiologist, Doctor of Audiology            [name]            [name]  [contact] [contact]

Study Centre(s):	
The testing will take place at a single site in Bern, Switzerland at the Bernafon AG headquarters.

Statistical Considerations:	
The analysis and documentation will be performed by the statistician using the latest validated R version with R Studio as IDE. Appropriate data analysis will be performed with parametric and non-parametric tests on questionnaire outcomes, hearing threshold measures, and music perception measures.

GCP Statement:	
This study will be conducted in compliance with the protocol, the current version of the Declaration of Helsinki, the ICH-GCP or ISO EN 14155 (as far as applicable) as well as all national legal and regulatory requirements.

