## **6.1 Methods of minimising bias**

### **6.1.1 Randomization**

A randomized assignment of the position of SP and IP will be used for the field trial period that includes P2 and P3 and consequently the lab tests. The position of the SP and the IP (as either program 2 or 3) will be based on a list created by the statistician. This reduces bias by using a different scroll position as the earlier position has a better chance of scoring higher due to the more prominent placement and likelihood that subjects might not always scroll to the 3rd program. The randomization list will not be concealed from the PI but should be in the ISF so that the PI knows in which condition order to test each subject.

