### 7.2 Recruitment and screening

Bernafon has its own directory of test subjects that use the Bernafon clinic for updated fittings and general maintenance of their hearing aids. These test subjects do not consist of employees of Bernafon or family members of employees. The test subjects for the current study will first be chosen from the internal subject directory. Once the appropriate options from the internal list have been exhausted, a flyer with information about the trial will be shared with musical groups/orchestras within a 20 km radius of the city of Bern. The flyer will provide the email address of the PI of the study for further information. Additionally, participants may be recruited by word of mouth. If a current person from the directory or someone that is enrolled for the current study knows of another person with hearing loss, they may give them the contact information of the PI. The prospective person can then contact the PI if they wish to have more information and/or to make a screening appointment to determine if they're eligible to participate in the study. The PI will respond by email or phone (whichever is the preference of the possible test subject). The PI of the study is well informed and qualified to answer all questions and give information about the study. If there are any medical indications suspected during the screening, the subject will be recommended to see a physician and then return if there are no contraindications for hearing aids. During the screening discussion it will be determined whether the person

is cognitively able to act on their own behalf. Additionally, if the person comes alone or if they are accompanied will help to determine their level of independence. It will be explained to the subjects that the general compensation for their time is by means of a box of batteries and cleaning accessories.

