### 9.2.2 Assessment of secondary outcomes

The Adaptive Music Perception (AMP) test will be run in the lab. The test is designed to assess aspects of music including meter and timber. The test is a computerized two-alternative forced-choice method run on a touch screen. The adaptation process uses a two-down, one-up rule and the score is the average of the last four reversal points. A reversal point is when the subject makes a correct selection and the adaptation reverses to a lower level.

They will also complete a product questionnaire with specific questions about feedback, sound quality, and unexpected behaviour for the general P1 program. The questionnaire is given to them to take home at the first appointment to be filled out and returned at the second appointment. The questions are rated with either a 5-point scale with 1 being the most positive outcome or yes/no answers. They will complete a music perception questionnaire for all three programs. The questions are rated with a visual analogue scale (VAS). The music questionnaire for P1 will be given to them at the first appointment and returned at the second. The music questionnaires for P2 and P3 will be given to them at the second appointment and returned at the third.

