### **9.3 Procedures at each visit**

#### **9.3.1 Screening/First visit**

Screening visit, Day 0: The potential participants will be given the Patient Information and Informed Consent form. The trial will be explained including how many visits are expected as well as the type of testing that they will complete. They are given time during the appointment to read the information and decide whether to participate in the study. If they choose to not take part in the study, they will not sign the consent form, and the appointment will finish. If they choose to join the trial, they will sign and date the consent form. No trial activities will be performed before the consent form is signed and dated by the subject and the investigator. Subjects will receive a copy of the signed consent form. A hearing history is then taken, and otoscopy is performed. A hearing test is performed, and inclusion/exclusion criteria will be determined. The subject is then randomized regarding the assignment of the music programs (IP or SP) to program slots 2 or 3. They are fitted with the IMD based on a first fit in the software and adjusted using REM data to match the gain targets. The hearing aids will be fit only with a general program in the P1 slot. They will perform the lab test with the AMP in two conditions: unaided and aided with the general program. They are given an IFU for the hearing device. They are given a product questionnaire and a music perception questionnaire and instructed to complete them at home a day before their next appointment. Any AEs are reported in the CRF. They are scheduled for the second visit.

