#### **9.3.2 Fitting/Second visit**

Fitting Visit, Day 10 +/- 7: Otoscopy is performed, and the subjects return the completed questionnaires. The IMDs are fitted with IP and SP as specified by the randomization carried out at the first visit. The IP is optimized and fine-tuned based on comments that the subject makes about the sound while they play their instrument in the clinic. The SP is programmed without any adjustment based on the default music program offered in the software. They are instructed to switch between programs two and three when playing and listening to music for the next 10 +/- 7 days. They perform the lab test with the AMP in one condition: aided with P2. The subjects are given the music perception questionnaires and instructed to complete them at home a day before their next appointment. One questionnaire pertains to P2 and the other to P3. Any AEs are reported in the CRF. They are scheduled for the third visit.

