#### **9.3.3 Lab/Third visit**

Final Visit, Day 20 +/- 7: Otoscopy is performed. The subjects return the completed product questionnaires. They perform the lab test with the AMP in one condition: aided with P3. They complete a preference questionnaire during the appointment. They are notified that the trial has ended and those that normally wear hearing aids can return to using their own devices. They will return the IMD to the clinic. Any AEs are reported in the CRF. Those that are on the Bernafon subject list and normally wear devices fitted by the Bernafon clinic are reminded to return to the clinic for normal maintenance of their hearing aids. Anyone that would like to join the Bernafon clinic are also welcome to do so.

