3.2 Randomization

The study is based on repeated measures with the SP and the IP. Participants are asked to switch between the listening programs in a given condition (practice, rehearsal, or concert) in order for them to gather comparable experiences while playing and listening to music.

Program allocation effect, i.e. higher likelihood to use program 2 than 3, will be compensated by randomizing the order of the tested protocols in the listening program slot. This risk is outbalanced by the benefit of directly comparing the same listening situation with both programs.

The program order will be randomized, and the lab test order will follow the program order randomization. The active participation of the investigator is required for the IP resulting in a single blind (participant only) design. The randomization list will be provided to the investigator by the statistician and documented before the recruitment process starts.

The randomization list will be generated with a random permuted block method and a random digit link to control any potential order inequality. Pocock (1983, p 77) provides a link between random digits and the structure of blocks for four patients and 2 treatments (order). No stratification is foreseen because no confounding factors have been identified at this stage of the study design.

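### The primary preference form is completed at visit 3, where staff who know the program slots are present, while the other questionnaires are completed at home; nothing in the plan keeps those staff away from its completion

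*Protocol*

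**What the plan says.** **Primary form.** The synopsis puts it at the end of the trial: "At the end of the trial the participants will complete a preference questionnaire and choose a preferred program". Protocol 9.3.3 (third visit) is more specific: "They complete a preference questionnaire during the appointment". The schedule in 9.1 also marks it at visit 3.

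**Other questionnaires.** Protocol 9.3.1 covers the product form and the music form for the general program: "They are given a product questionnaire and a music perception questionnaire and instructed to complete them at home a day before their next appointment". Protocol 9.3.2 covers the music forms for programs 2 and 3: "The subjects are given the music perception questionnaires and instructed to complete them at home a day before their next appointment". Section 9.2.2 agrees. (Section 9.3.3 calls the forms returned at visit 3 product questionnaires; 9.2.2 and 9.3.2 show they are the program 2 and 3 music forms. Either way they come from home.)

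**Who knows the allocation.** Protocol 6.1.1: "The randomization list will not be concealed from the PI". Section 6.2 keeps the list in the site file for the investigator's use. SAP 3.2 gives the reason: "The active participation of the investigator is required for the IP resulting in a single blind (participant only) design". Participants are told only that slots 2 and 3 hold music programs (Protocol 6.2).

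**Contact and expectation.** The IP is tuned at visit 2 from the participant's remarks while playing (9.3.2). The principal investigator collects adverse events at every visit (10.1). Protocol 3.1 expects the IP to do better on perception and on preference.

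**The concern.** The primary outcome is a self-report, and it is the one questionnaire that the plan has filled in at the clinic rather than at home. At that visit the participant meets staff who may know which slot holds the IP and whose protocol expects the IP to win.

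Someone who knows the slot can cue without meaning to: by tone, by how the scale is explained, or by a follow-up question. Such a cue points to the IP in whichever slot it sits, so randomising the slot does not cancel it. The primary test sees only the score and cannot separate a cued answer from a real preference. That test, at two-sided 0.05, is meant to answer the first and second research questions (Protocol 11.4.2; SAP 4.1 and 6.2.1).

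**Working it through.** **1. Outcomes side by side**

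| Outcome | Where completed | Source |
|---|---|---|
| Product questionnaire | Home, before visit 2 | Protocol 9.3.1 |
| Music questionnaire, general program | Home, before visit 2 | Protocol 9.3.1 |
| Music questionnaires, programs 2 and 3 | Home, before visit 3 | Protocol 9.3.2 |
| Music perception (AMP) test | Clinic; "The test is a computerized two-alternative forced-choice method run on a touch screen" | Protocol 9.2.2 |
| **Preference (primary)** | **Clinic, during visit 3** | Protocol 9.3.3 |

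The AMP is also measured in the clinic, but it is a computerised threshold test, not an opinion given on a form.

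**2. What the safeguards cover**

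- Slot randomisation addresses the advantage of the earlier scroll position (Protocol 6.1.1).
- Participant masking stops a participant from knowing, unaided, which answer favours the IP.
- Neither stops a cue from a person who knows the slot.
- The stated reasons for an open investigator are fitting the IP (SAP 3.2) and knowing the test order (Protocol 6.1.1). Neither reason requires that person to be present when a self-report is completed.
- No section asks for unattended completion, masked staff, a neutral script or sealed return of this form.

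**3. Illustration of size**

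The plan gives no figure to reproduce: 18-20 participants was set without an effect size or power calculation (SAP 3.3).

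*From the documents:* n = 20 (upper end of the range); scores -2 to +2 for the five categories from SP much better to IP much better; two-sided signed-rank test at 0.05.

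*Assumed:* no true preference, with category probabilities 10/25/30/25/10%; a share q of participants moved one category toward the IP, the top category staying put.

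The probability of category k becomes (1 - q)p(k) + q·p(k - 1), and the top category also keeps its own q·p. For q = 0.20:

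- SP much better: 0.8 × 0.10 = 0.08
- SP better: 0.8 × 0.25 + 0.2 × 0.10 = 0.22
- No difference: 0.8 × 0.30 + 0.2 × 0.25 = 0.29
- IP better: 0.8 × 0.25 + 0.2 × 0.30 = 0.26
- IP much better: 0.10 + 0.2 × 0.25 = 0.15

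For the test, zeros are dropped, leaving m scores. V is the sum of midranks of the positive scores, with mean m(m+1)/4 and variance m(m+1)(2m+1)/24 - Σ(t³ - t)/48 over tie groups of size t. A continuity correction of 0.5 is used. With five categories and n = 20 there are C(24,4) = 10,626 possible count patterns, so the rejection rate can be summed exactly:

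| Share moved (q) | Significant for IP | Significant for SP | Two-sided total |
|---|---|---|---|
| 0 | 2.2% | 2.2% | 4.3% |
| 10% (about 2 of 20) | 4.6% | 0.9% | 5.5% |
| 20% (about 4 of 20) | 8.7% | 0.4% | 9.1% |
| 30% (about 6 of 20) | 15.1% | 0.1% | 15.2% |

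(Rows may differ from their sum by rounding.) At n = 18 the totals are 4.2, 5.2, 8.3 and 13.6%. Null distributions of 10/20/40/20/10% and 10/30/20/30/10% give 9.2% and 9.0% at q = 20%, n = 20, so the result depends little on the assumed shape. It depends heavily on q, which is unknown.

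**The case against.** **Presence of the investigator.** A reader might infer that the form is filled in with the unmasked fitter in the room. The documents do not say so; they say only that it happens during the appointment. Protocol 12.1.1 and 12.1.2 mention site staff and other investigators, so the person who tuned the IP need not be the one handing over the form. The questionnaires are an appendix that is not in the documents, so their instructions and labels cannot be checked. This stands. The point is that nothing prevents it, not that it is prescribed.

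**Pressure on participants.** A reader might infer that many participants depend on the sponsor's clinic and would want to please. Protocol 7.2 says "The test subjects for the current study will first be chosen from the internal subject directory", then turns to musical groups and word of mouth. It gives no numbers and says these people use the clinic, not that they depend on it. A masked participant also cannot aim to please without recognising the IP or being cued. The concern does not rest on this.

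**Sponsor employment and data entry.** That the investigator is a sponsor employee can only be inferred from the role and the site. Entering the result in the case report form is transcription after the answer exists and is not a route for cueing.

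**A partial check already exists.** The home-completed program 2 and 3 music ratings carry a planned IP versus SP contrast (SAP 6.2.3). A preference with no echo there would be visible. This stands and is used in the fix.

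**Completeness.** Nothing is imputed (Protocol 11.5), the analysis population needs primary outcome data (11.4.1), and n is small. In-clinic completion protects against lost forms. Completion alone on arrival keeps that benefit.

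**Exploratory trial.** The synopsis and SAP 3.1 say so, which limits the harm. The primary outcome is still tested at 0.05 to answer two research questions.

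**Conclusion.** The concern holds as an avoidable risk of bias in how the primary outcome is collected. The plan places the preference form in an appointment where people who know the slot are likely to be present, does not say who administers it, and does not keep them away, although it already uses home completion for the other questionnaires.

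The documents do not show that cueing would occur or that the result would be biased, and a reader should not infer either. The likely direction is toward the IP. The size is unknown. On the assumptions above, a one-category shift in 20% of participants would roughly double the two-sided rejection rate, from about 4% to about 9%. A shift in 10% would change that total little (about 5.5%), although the part favouring the IP would go from 2.2% to 4.6%. This is a cheap improvement worth making, not a flaw that invalidates the design.

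**What to change.** Amend Protocol 9.3.2, 9.3.3 and the study schedule:

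- Add the preference form to the visit 2 take-home pack, with the music forms for programs 2 and 3.
- Word it as 'program 2' and 'program 3'. The statistician recodes the answers to SP and IP from the randomisation list.
- The participant completes it at home the day before visit 3 and hands it over sealed, before any discussion of the programs.
- Anyone who arrives without it completes it alone before meeting the investigator.

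Add one line to SAP 6.2.1: report, descriptively and per participant, whether the preference agrees in direction with the IP minus SP difference in the home-completed music ratings.

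**Cost.** Some wording and one more sheet in an existing pack; no extra visit or staff. An occasional forgotten form is covered by the fallback.

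**Limit.** Cues given while the IP is tuned at visit 2 would remain and could colour the home ratings as well. Agreement between the two would therefore be reassuring but not proof.
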